2.5.4.2 Sensitivity analysis

A sensitivity analysis will be performed on the mFAS population using the same ANCOVA model and the same rules for handling intercurrent events as for the primary analysis.

2.6 Analysis of the key secondary objective

Not applicable.

2.7 Analysis of secondary efficacy objective(s)

The following secondary efficacy variables will be evaluated for the FAS:

2.7.1 Testing of superiority with regard to NRS at Week 12

To compare the efficacy of EMA401 over placebo in 24-hour average pain intensity score at Week 12, using an 11 point Numeric Rating Scale (NRS). This comparison will be done by testing the null hypotheses of superiority of EMA401 25 mg or over placebo and of EMA401 100 mg over placebo while adjusting for multiplicity. Multiplicity adjustment for the pairwise comparisons will be performed using the Hochberg procedure. Based on the set of candidate models as specified in Section 2.5.2 trend tests will be performed to evaluate the existence of a dose-response effect using MCP-mod.

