- **Permanent discontinuation of study treatment due to AE, LoE and use of prohibited medication:** If retrieved drop-out data are available, these will be used for analysis. If no data was retrieved after study treatment discontinuation, missing data will be multiply imputed based on placebo arm data, i.e. “jump to reference” (J2R) assumption for the EMA401 arms, missing at random assumption for placebo arm ([Carpenter, Roger, and Kenward 2013](#)). More details on the imputation model will be specified in the statistical analysis plan prior to unblinding.
- **Permanent discontinuation of study treatment due to other reasons than AE, LoE and use of prohibited medication:** If efficacy data collected after study treatment discontinuation are available (retrieved drop-out), then the retrieved drop-out data will be excluded and missing data after study treatment discontinuation will be multiply imputed using the MAR assumption.

The multiple imputations will be carried out on the weekly mean pain score.

The primary objective will be achieved if the null hypothesis of flat dose-response curve (where all dose means are equal to the placebo mean) at Week 12 is rejected using $\alpha=0.025$ one-sided. The null hypothesis of a flat dose-response curve will be tested using Multiple Comparison Procedure – Modelling (MCP-Mod) with three E_{\max} and 2 sigmoidal- E_{\max} dose response models as the candidate shapes. The following ED_{50} (the dose at which half of the maximum effect is reached) values will be used for the E_{\max} models: 17, 80, and 200. The parameters of the sigmoidal E_{\max} models (ED_{50} , h) will be as follows: (77, 3) and (175, 1.5), where h is the Hill parameter that determines the steepness of the dose-response shape. The MCP-Mod dose response test will be performed at each post-baseline visit. No multiplicity adjustment by visit will be carried out.

Dose-response estimation will be performed based on the ANCOVA least square estimates using MCP-Mod as described in [Pinheiro et al \(2014\)](#). The same candidate models as above will be used in a model averaging approach to obtain an estimate of the dose-response curve.

The same ANCOVA model will be applied at the visits prior to Week 12.

Summary statistics by treatment and visit will be provided for the primary efficacy variable.

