The primary analysis on the change from baseline to Week 12 in the weekly mean of the 24-hour average pain score will be performed as originally planned. Besides the primary estimand, which is of main clinical interest, the supplementary estimand, which provides insight into the magnitude of improvement in efficacy that might be achieved if all patients were able to take EMA401 as prescribed for 12 weeks, will be analysed. The other planned supplementary estimands will be dropped, as they are of minor interest in the situation with many study treatment discontinuations due to trial termination in the scope of the Urgent Safety Measures (USM).

To support the primary analysis and to get an idea about the effect that might be achieved if the trial had not been terminated and if all patients had the chance to complete the Week 12 assessment, a sensitivity analysis on a modified population will be performed. The modified full analysis set will include all patients who had a chance to complete the study before the termination date, i.e. who had been randomized at least 12 weeks before study termination date.

Due to the considerably reduced number of patients who completed the study, only descriptive subgroup analyses will be provided. Moreover, most of the secondary [REDACTED] endpoints will also be summarized descriptively only. [REDACTED]

1 Introduction

This statistical analysis plan (SAP) describes all planned analyses for the Clinical Study Report (CSR) of study CEMA401A2201, a Phase 2, double-blind, placebo-controlled, randomized dose ranging trial to determine the safety and efficacy of three dose levels of EMA401 in reducing 24-hour average pain intensity score in patients with post-herpetic neuralgia.

The content of this SAP is based on the final version of protocol CEMA401A2201 Amendment 1 (release date 14-May-2018). All decisions regarding final analysis, as defined in the SAP document, have been made prior to database lock and unblinding of the study data.

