If the 300 mg b.i.d dose would have been initiated: The primary objective would have been achieved if the null hypothesis of flat dose-response curve (where all dose means are equal to the placebo mean) at Week 12 is rejected using $\alpha=0.025$ one-sided. The null hypothesis of a flat dose-response curve will be tested using Multiple Comparison Procedure – Modelling (MCP-Mod) with three E_{\max} and two sigmoidal- E_{\max} dose response models as the candidate shapes. The following ED_{50} (the dose at which half of the maximum effect is reached) values will be used for the E_{\max} models: 17, 80, and 200. The parameters of the sigmoidal E_{\max} models (ED_{50} , h) will be as follows: (77, 3) and (175, 1.5), where h is the Hill parameter that determines the steepness of the dose-response shape. The MCP-Mod dose response test will be performed at each post-baseline visit. No multiplicity adjustment by visit will be carried out.

Dose-response estimation will be performed based on the ANCOVA least square estimates using MCP-Mod as described in Pinheiro et al (2014). The same candidate models as above will be used in a model averaging approach to obtain an estimate of the dose-response curve. The final estimate of the dose-response curve is the median of the dose-response curves obtained.

The same ANCOVA model will be applied at the visits prior to Week 12.

Summary statistics for absolute values and change from baseline by treatment and visit will be provided for the original measurements (i.e. the raw data prior to multiple imputation) of the primary efficacy variable. If a measurement is collected under the period of use of prohibited medications or the 7 days thereafter, it will be excluded from the summaries. [REDACTED]

In the event the EMA401 300 mg b.i.d. dose cannot be initiated, the trend tests deduced from the set of candidate models will be performed but the dose response estimation will not be performed. In that case, the first secondary objective will be evaluated to compare the efficacy of the remaining doses of EMA401 over placebo in 24-hour average pain intensity score at Week 12, using an 11 point Numeric Rating Scale (NRS). This comparison will be done by

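### With no 300 mg arm, does keeping the MCP-Mod trend test beside the Hochberg comparisons leave the efficacy conclusion undefined?

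*SAP*

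**What the plan says.** Protocol 9.4.2 makes the MCP-Mod test the criterion for the primary objective: "The primary objective will be achieved if the null hypothesis of flat dose-response curve" at Week 12 is rejected at one-sided 0.025. For the case without a 300 mg arm, the same section drops dose-response characterization and turns to the first secondary objective, superiority over placebo, tested pairwise with Hochberg. It gives no level for that fallback.

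SAP 1.1 confirms that the 300 mg arm was not initiated. SAP 2.5.2 then makes the primary success rule conditional: "If the 300 mg b.i.d dose would have been initiated: The primary objective would have been achieved" on rejection at one-sided 0.025. For the three-arm case it says that "the trend tests deduced from the set of candidate models will be performed but the dose response estimation will not be performed", and that the first secondary objective is evaluated to compare the remaining doses with placebo.

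SAP 2.7.1 repeats the arrangement. It opens with the comparison of efficacy against placebo and states two hypotheses, one per dose. It continues "Multiplicity adjustment for the pairwise comparisons will be performed using the Hochberg procedure" and then adds that, from the same candidate models, "trend tests will be performed to evaluate the existence of a dose-response effect using MCP-mod".

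The SAP's Amendment 1 text says that the primary analysis of the change in the weekly mean of "the 24-hour average pain score will be performed as originally planned". SAP Section 4, which lists changes from the protocol, does not mention the trend test.

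**The concern.** Two inferential procedures act on one variable at one time point. The trend test appears under the primary objective in SAP 2.5.2 and under a secondary objective in 2.7.1, while its success rule is worded for a situation that did not occur. Neither document states a level for Hochberg. If one procedure were significant and the other not, a reader might ask whether efficacy had been shown, and an answer settled after unblinding could be biased. Allowing either result to count would also raise the type I error above 2.5%.

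The protocol's three-arm rule drops dose-response characterization, which arguably includes the test, so keeping the test looks like a departure that Section 4 should have listed.

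**Working it through.** **1. Inputs.** From SAP 2.5.2: Emax shapes with ED50 17, 80 and 200; sigmoid Emax shapes (77, 3) and (175, 1.5). From SAP Section 3: SD 2.6, effect 1.0 at 300 mg b.i.d., 90 per arm, one-sided 0.025, power at least 77%. From the SAP's Amendment 1 text and Section 1.1: 129 randomized 1:1:1, so 129/3 = 43 per arm if evenly split (an assumption). Also assumed: complete data, and one-sided 0.025 for both procedures.

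**2. The plan's own figure.** The trend statistic is the maximum over the five shapes of T = Σcᵢȳᵢ / (s√(Σcᵢ²/nᵢ)), with cᵢ proportional to nᵢ(μᵢ − μ̄), compared with a simulated multivariate-t critical value. Improvement is counted as positive. With four arms of 90, simulated power for the five shapes is 76.8, 77.4, 77.2, 85.4 and 78.5% if the ED50s are in mg b.i.d. (minimum 76.8%), and 79.4, 77.9, 76.7, 87.1 and 79.0% if they are in mg/day (minimum 76.7%). The stated 77% is reproduced on either scale.

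**3. Three arms, the two procedures.**
- Trend: reject if the maximum T exceeds 2.203 (mg b.i.d.) or 2.186 (mg/day), on 129 − 3 = 126 df.
- Hochberg: each dose is compared with placebo, with standard error 2.6 × √(2/43) = 0.561. Both doses are claimed if both p ≤ 0.025; otherwise one is claimed if its p ≤ 0.0125.

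**4. All means equal** (2 million draws, mg b.i.d.). Trend rejects in 2.50%, Hochberg in 2.40%, trend only in 0.98%, Hochberg only in 0.88%.
- Either: 2.50 + 0.88 = 3.38%.
- Disagreement: 0.98 + 0.88 = 1.86%.

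On mg/day these are 3.27% and 1.64%. The Bonferroni bound is 5.0%; the excess over 2.5% is well below it because the two statistics are highly correlated.

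**5. Planning shapes** (mg b.i.d., 43 per arm). From trend T, Hochberg H and disagreement D, trend-only is (D + T − H)/2 and Hochberg-only is the rest of D.

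| Shape | Trend % | Hochberg, any dose % | Disagree % | Trend only % | Hochberg only % |
|---|---|---|---|---|---|
| Emax 17 | 33.8 | 32.2 | 7.6 | 4.6 | 3.0 |
| Emax 80 | 22.9 | 18.4 | 6.9 | 5.7 | 1.2 |
| Emax 200 | 16.2 | 12.2 | 5.9 | 5.0 | 0.9 |
| Sigmoid (77, 3) | 25.7 | 16.4 | 9.9 | 9.6 | 0.3 |
| Sigmoid (175, 1.5) | 12.0 | 8.3 | 5.1 | 4.4 | 0.7 |

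On mg/day the disagreement is 6.1-9.5%. The SAP expects "many study treatment discontinuations due to trial termination", so less information is likely. With an assumed effective 30 or 20 per arm, the either-test figure under equal means stays at 3.4%, and disagreement under the shapes is 4.3-7.8% or 3.7-6.1%.

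**6. Does the SAP really leave the roles open?** Set side by side, 2.5.2 and 2.7.1 attach the comparison of efficacy with placebo to the two pairwise hypotheses under Hochberg. They attach the trend test to the existence of a dose-response. The objectives table in SAP 1.2 keeps the same two aims apart. The success rule in 2.5.2 is confined to the case with 300 mg, so the natural reading is that no success claim hangs on the three-arm trend test. A significant trend with no significant pairwise test, the usual form of disagreement in the table, then has a plain meaning: evidence against a flat curve, with neither dose shown superior. Those are answers to two questions, not a conflict over one.

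**7. The level.** One-sided 0.025 is given for this test and these five shapes in 2.5.2 and again in Section 3. SAP 5.5.1.1 calls for 95% confidence intervals from the same ANCOVA, which match one-sided 0.025. An analyst would use that level for both procedures.

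**The case for a change.** The best case for a change is that a plan should not rely on inference from context. The SAP claims finality: "All decisions regarding final analysis, as defined in the SAP document, have been made prior to database lock and unblinding of the study data". Yet no sentence gives Hochberg a level or says in so many words which result supports efficacy. The Amendment 1 text says the primary analysis is unchanged, although the protocol's original plan for three arms is the Hochberg fallback. Protocol 9.4.2 defines success on the characterization objective by the test, so dropping characterization reasonably means dropping the test. A few sentences would settle all this at little cost.

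Part of this stands. The Hochberg level is unstated in both documents, the trend test's three-arm role is not labelled, and Section 4 is incomplete if characterization includes the test. That last reading is plausible but not forced: Protocol 9.4.2 describes the flat-curve test and dose-response estimation in separate paragraphs and never says the test is dropped, and the SAP takes only the estimation to fall away. The retained test is openly stated in two SAP sections, so its absence from Section 4 is a listing slip.

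Redesignating the basis for a claim is a trade-off. Resting any claim on Hochberg alone costs 1.6-9.3 points against the trend test (33.8 − 32.2 up to 25.7 − 16.4). Closed MCP-Mod in place of Hochberg would gain 0.8-4.5 points for any dose (33.0 − 32.2 up to 20.9 − 16.4) and lose 0.3-2.9 points for 25 mg (2.4 − 2.1 up to 16.8 − 13.9), on the mg b.i.d. scale.

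**Conclusion.** No change to the plan follows. Run as written at one-sided 0.025, the two procedures give valid answers to two distinct questions, with error rates of 2.5% and 2.4% under equal means. The 3.3-3.4% figure belongs to an either-test rule that neither document contains. Disagreement in roughly 5-10% of trials under the planning shapes is what tests of different hypotheses produce, and it can be reported as such.

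Explicit wording would mostly restate roles the SAP already assigns, and a line in Section 4 would alter no result. The setting also limits what is at stake: a terminated Phase 2 trial with 129 of 360 planned patients and an abbreviated report. The figures rest on an even split of 43 per arm, complete data, SD 2.6, the five planning shapes and 0.025 for both procedures. The conclusion about roles rests on the text of SAP 2.5.2 and 2.7.1, not on those assumptions.

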2.7.2 Responder Analysis

Responder analyses (based on at least a 30%, 50% improvement from baseline on NRS) will be performed in order to facilitate the interpretation of the results of the primary and supplementary analyses from a clinical relevance perspective. These analyses will be performed on the FAS population. One secondary estimand is considered, together with one supplementary estimand.

The secondary estimand and the supplementary estimand to the secondary estimand differ from the primary and supplementary estimands in two ways:

- First, the variable of interest is the responder status in NRS score, with response status corresponding to at least a 30% (50%) improvement in pain from baseline.
- Second, the measure of intervention effect is the odds ratio of the proportions of responders between investigational drug and placebo.

The other features characterizing these responder analyses are exactly the same as for the primary and the supplementary analysis, respectively.

From an analysis point of view, the responder status for each patient will be calculated on the continuous weekly score measurements after missing data are multiply imputed based on the approach specified corresponding to the primary analysis and the supplementary analyses. If the patient is a completer but week 12 measurement is affected by the changes in doses of concomitant medication for PHN or the use of prohibited medication then the responder criteria will be defined based on the multiply imputed values by MAR. The resulting responder variable will be analyzed using a logistic regression model including all randomized patients and adjusting for the same covariates as the ANCOVA model for the primary analysis.

From an analysis point of view, the resulting responder variables will be analyzed using a logistic regression model including all randomized patients (FAS population) and adjusting for the same covariates as the ANCOVA model for the primary analysis. Odds ratios will be estimated along with their 95% CIs.

The responder analyses will be performed for each visit, with the obvious modification in the definition for the week of interest.

2.7.3 Other secondary efficacy objectives

1. BPI-SF interference total score will be summarized descriptively by treatment and visit.
2. Weekly mean of the 24-hour **worst** NRS pain score, using an 11-point Numeric Rating Scale (NRS). This variable will be summarized descriptively by treatment and visit.
3. Number of patients in each level of PGIC at Week 12 will be presented by treatment. PGIC classification will also be combined into two categories: Either a "very much improved" or a "much improved" reported, and the five remaining categories.
4. Change from baseline to Week 4, Week 8 and Week 12 in NPSI. The total score NPSI (sum of 10 descriptor items) variable will be analyzed according to the same ANCOVA model as the one used for the primary variable. NPSI total score will also be summarized descriptively by treatment and visit. The same supplementary analysis as for the primary endpoint will be performed. Multiple imputation will be carried out in a similar fashion as for the primary analysis of the NRS pain score. The 5 dimensions of pain (burning pain, deep/pressing pain, paroxysmal pain, evoked pain, paraesthesia/dysesthesia) will be summarized descriptively by treatment and visit in the double-blind treatment epoch.
5. Insomnia Severity Index (ISI) will be summarized descriptively by treatment and visit.

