9.4.2 Statistical model, hypothesis, and method of analysis

The aim is to estimate the treatment effect of the investigational drug (EMA401) compared to placebo, for the target population on the primary pain parameter. The definition and the justification of the corresponding primary estimand, as well as the definition of the supplementary and secondary estimands are detailed in an Estimand Charter.

The primary estimation method is based on an Analysis of Covariance (ANCOVA) model including region (e.g. US, EU), treatment, sex, use of concomitant pain medication for PHN (yes/no) as factors and baseline (mean pain intensity) score and age as covariates. The analysis will account for different post-randomization events as follows:

- **Changes in doses of concomitant medication for PHN:** Efficacy observations collected during the period of changes in doses of concomitant medication for PHN (compared to

baseline) and the 2-days thereafter will be excluded, since they are considered affected by the concomitant medication dose change. The resulting missing data after this step will be multiply imputed using the Missing at random (MAR) assumption.

- **Intake of rescue medication:** Efficacy data collected during intake of rescue medication will be used for analysis.
- **Intake of prohibited medications with potential confounding effect prior to study treatment discontinuation:** The prohibited medications with a potential confounding effect are defined as those listed in [Table 5-2](#) requiring study treatment discontinuation. Efficacy observations collected during the intake period of such prohibited medications and the 7-days thereafter will be excluded, since they are considered affected by the prohibited medication intake. The resulting missing data after this step will be multiply imputed using the MAR assumption.

The design feature of retrieved drop-outs, considered in order to minimize the occurrence of missing data on primary pain parameter, is exploited for the statistical analysis as follows:

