2.5.2 Statistical hypothesis, model, and method of analysis

The aim is to estimate the treatment effect of the investigational drug (EMA401) compared to placebo, for the target population on the primary pain parameter. The definition and the justification of the corresponding primary estimand, as well as the definition of the supplementary and secondary estimands are detailed in the Estimand Charter.

The primary estimation method is based on an Analysis of Covariance (ANCOVA) model including region (America or Europe and Australia, Asia), treatment, sex, use of concomitant pain medication for PHN (yes/no) as factors and age and baseline (mean pain intensity) score as covariate. The analysis will account for different intercurrent events (i.e. events that occur post-randomization) as follows:

- **Changes in doses of concomitant medication for PHN:** Efficacy observations collected during the period of changes in doses of concomitant medication for PHN (compared to baseline) and the 2-days thereafter will be excluded, since they are considered affected by the concomitant medication dose change. The resulting missing data after this step will be multiply imputed using the Missing at random (MAR) assumption.
- **Intake of rescue medication:** Efficacy data collected during intake of rescue medication will be used for analysis.

- **Intake of prohibited medications with potential confounding effect prior to study treatment discontinuation:** The prohibited medications with a potential confounding effect are defined as those listed in Table 2-1 requiring study treatment discontinuation. A list of prohibited medications is available at the following [REDACTED]

[REDACTED] Efficacy

observations collected during the intake period of such prohibited medications and the 7-days thereafter will be excluded, since they are considered affected by the prohibited medication intake. The resulting missing data after this step will be multiply imputed using the MAR assumption.

Table 2-1 Prohibited medication

Medication	Prohibition period	Action taken for study treatment
Prohibited prior to Randomization and throughout study		
High dose capsaicin patch (8%)	3 months prior to Randomization and after Randomization	Discontinue study treatment
Prohibited 2 week prior to Randomization and throughout the study		
Any skeletal muscle relaxant (e.g. baclofen, orphenadrine, methocarbamol)	2 weeks prior to Randomization and after Randomization	None

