5.4.5 Neuropathic Pain Symptom Inventory (NPSI)

The Neuropathic Pain Symptom Inventory (NPSI) is a 12 item patient reported outcome measure that contains 10 descriptors representing 5 dimensions of pain (burning pain, deep/pressing pain, paroxysmal pain, evoked pain and paraesthesia/dysesthesia) and 2 temporal items designed to assess pain duration and the number of pain paroxysms. The score is recorded at Visits 101, 104, 106, 199, 201 and TD visit.

The sum of the responses to the 10 questions (all except qn. 4 and qn. 7) will be regarded as the total score and will be used for the analysis.

[figure not shown]
The dimensional score of each of the five dimensions are calculated as follows :

[figure not shown]
[figure not shown]
[figure not shown]
- Burning = Q1
- Pressing = (Q2 + Q3) /2
- Paroxysmal = (Q5 + Q6) /2
- Evoked = (Q8 + Q9 + Q10) /3
- Paraesthesia / dysesthesia = (Q11 + Q12)/2

[figure not shown]

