5.5.1 Primary analysis

5.5.1.1 ANCOVA

The primary analysis (and all other analyses of continuous variables) will be done using analysis of covariance. The model is:

mean pain score = intercept + region + treatment + sex + age + PHNmed (yes/no) + baseline (mean pain intensity) + error.

The SAS procedure MIXED will be used for computing p-values and 95% confidence intervals for LS means.

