5.5.1.2 Missing data imputation

For the purpose of missing data imputation, the following two scenarios will be considered:

- Jump to reference (J2R)
- Missing At Random (MAR)

The imputation will be based on all available data (i.e. from all scheduled time points) using all covariates as specified in the ANCOVA model. For J2R only placebo data will be used, for MAR data from the same treatment arm will be used for building the imputation model.

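### Read literally, the NPSI ANCOVA adjusts for baseline NRS pain and does not name baseline NPSI; the cost is precision only, and one sentence would settle it

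*SAP*

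**What the plan says.** - SAP 2.7.3 item 4 takes change in NPSI total score at Weeks 4, 8 and 12 and says that it "variable will be analyzed according to the same ANCOVA model as the one used for the primary variable". Protocol 9.5.1 item 6 uses the same wording for Week 12.
- SAP 5.5.1.1 gives the model once: "The primary analysis (and all other analyses of continuous variables) will be done using analysis of covariance". The terms are region, treatment, sex and age, then "PHNmed (yes/no) + baseline (mean pain intensity) + error". The outcome is written as the mean pain score.
- The method text for the primary variable names the same baseline term: "age and baseline (mean pain intensity) score as covariate" in SAP 2.5.2 and "baseline (mean pain intensity) score and age as covariates" in Protocol 9.4.2. Both refer to the NRS diary score.
- SAP 5.5.1.2 builds the imputation from data at all scheduled time points, "using all covariates as specified in the ANCOVA model". SAP 2.7.3 item 4 says NPSI is imputed in a similar way to the NRS score.
- Baseline NPSI exists. SAP 5.4.5 says: "The score is recorded at Visits 101, 104, 106, 199, 201 and TD visit". Visit 101 is baseline.

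No section replaces the NRS baseline term with baseline NPSI for this endpoint, or adds baseline NPSI to it.

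**The concern.** An ANCOVA of change gains most of its precision from the endpoint's own baseline. Baseline NRS pain is related to NPSI but is usually a weaker predictor of NPSI change. Without baseline NPSI in the model, the regression-to-the-mean part of the change score stays in the residual.

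This deserves a line because of what amendment 1 of the SAP left in place. BPI-SF, worst NRS pain, PGIC and ISI are now descriptive, so NPSI is the only secondary efficacy endpoint not based on the NRS that keeps an inferential model. Of 360 planned patients, 129 were randomized, about 43 per arm at 1:1:1 (129/3). Precision is scarce, and the missing covariate is already in the database because the change score cannot be computed without it.

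The outcome is also ambiguous. SAP 2.7.3 models a change, while the formula in SAP 5.5.1.1 is written for a level. With the endpoint's own baseline in the model, the two give the same treatment contrast. Without it, they differ by the between-arm difference in baseline NPSI after adjustment for the other covariates.

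**Working it through.** **The plan's own figure.** The documents state no power, SD or correlation for NPSI. The only power figure is at least 77% for the primary NRS trend test (90 per arm, SD 2.6, maximum effect 1.0, one-sided alpha 0.025). Simulating the maximum contrast test over the five candidate shapes gives a minimum of 77.2% with doses coded 25/100/300 and 77.0% with daily doses 50/200/600. The figure reproduces. It concerns NRS and is unaffected by this point.

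**Notation, all values assumed.** NPSI has equal SD (set to 1) at baseline and Week 12.
- r = correlation of baseline with Week 12 NPSI
- q = correlation of baseline NRS with baseline NPSI
- k = correlation of baseline NRS with Week 12 NPSI

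**Residual variance of NPSI change.**
- Adjusted for baseline NPSI: 1 − r²
- Adjusted for baseline NRS: 2(1 − r) − (k − q)²
- NRS version minus NPSI version: (1 − r)² − (k − q)²

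The difference is positive whenever |k − q| is below 1 − r, and this holds in every row below. It shrinks as r rises.

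**Results with q = 0.4–0.6 and k = 0.25–0.35.** The extremes of (k − q)² are (0.25 − 0.6)² = 0.1225 and (0.35 − 0.4)² = 0.0025. The r = 0.8 row uses q = 0.5 and k = r × q = 0.4, so (k − q)² = 0.01.

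| r | Baseline NPSI | Baseline NRS | Variance saved |
|---|---|---|---|
| 0.4 | 0.84 | 1.2 − 0.1225 = 1.0775 to 1.2 − 0.0025 = 1.1975 | 22.0% to 29.9% |
| 0.5 | 0.75 | 0.8775 to 0.9975 | 14.5% to 24.8% |
| 0.6 | 0.64 | 0.6775 to 0.7975 | 5.5% to 19.7% |
| 0.8 | 0.36 | 0.39 | 7.7% |

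At r = 0.5 the standard error falls by 1 − √(0.75/0.8775) = 7.5% to 1 − √(0.75/0.9975) = 13.3%.

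**Wider grid.** With k = r × q, r from 0.3 to 0.8 and q from 0.3 to 0.7, using baseline NRS in place of baseline NPSI raises the variance by 6% to 49% (standard error by 3% to 22%). At r = q = 0.5 the ratio is 0.9375/0.75 = 1.25. A simulation of 20,000 two-arm trials with 43 per arm gave 1.26, with the mean estimated difference near the true zero under both models. In that case 43 patients per arm carry the information of 43/1.25 ≈ 34.

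**Power illustration.** A comparison with 80% power under baseline NPSI adjustment would have about 78% at a variance ratio of 1.05, 72.5% at 1.20 and 66% at 1.40.

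These figures assume complete data. With multiple imputation the gain would differ, and the documents do not allow it to be quantified.

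**The case against.** The strongest reply is that SAP 5.5.1.1 is a template. Its outcome is written as the mean pain score, so applying it word for word to "and all other analyses of continuous variables) will be done using analysis of covariance" would give the NPSI analysis an NRS outcome. The reader must substitute the endpoint on the left, and may fairly do so on the right as well. SAP 2.1.1 also defines baseline generically for efficacy evaluations. SAP 5.5 places the SAS code in the table shells, and SAP 2.5.2 refers estimand definitions to the Estimand Charter. Neither is available, and either may already name baseline NPSI.

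This reading is plausible and lowers confidence. It does not remove the point. The baseline term names a specific score, and nothing tells the reader to replace it. Where the authors wanted an adaptation, they said so: SAP 2.7.2 notes it when extending the responder analysis to other visits.

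Three further replies stand:

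- Because the outcome is change, baseline NPSI is already subtracted from it. What remains is the regression-to-the-mean part, not the whole of any chance imbalance.
- A reader might infer that the imputation also leaves out baseline NPSI. SAP 5.5.1.2 does not support that. Its reference to data at all scheduled time points may already bring in Visit 101 NPSI.
- Little hangs on this endpoint. It is secondary, without multiplicity control or a stated power, in a terminated trial with an abbreviated report.

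**Conclusion.** The point holds as one of efficiency and clarity, at moderate confidence. Taken literally, the plan leaves a strong and freely available covariate out of the NPSI model. For the change score, naming it would save about 5 to 30% of residual variance if r lies between 0.4 and 0.6. The saving is about 8% in the example at r = 0.8, and it vanishes if the slope of Week 12 on baseline NPSI is 1. These figures rest on assumed correlations and equal SDs, since the documents give no NPSI data.

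Stronger readings are tempting but unsupported. A reader might infer a biased NPSI estimate or a false-positive risk; under randomization the choice between these covariates produces neither. A reader might infer that the main result is weakened; the primary NRS model already uses its own baseline. A reader might quote a fixed loss in patients; that describes one assumed set of correlations and is not a property of the plan. Nor do the documents establish that the programmed analysis omits baseline NPSI. They show only that the text does not name it.

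**What to change.** In SAP 2.7.3 item 4 and SAP 5.5.1.1, state that for NPSI the baseline covariate is the baseline NPSI total score. Baseline NRS pain may stay as an additional covariate. In SAP 5.5.1.2, confirm that baseline NPSI is included in the NPSI imputation model. If the substitution was always intended, the same sentence records it.

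The cost is one or two sentences of SAP text and at most one variable in the program, settled before unblinding. No new data are needed. The wording also removes the change-versus-level ambiguity.
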